1. AMENDMENT HISTORY

Amendment No.	Protocol Version No.	Date issued	Author(s) of changes	Details of Changes made

2. SYNOPSIS

Study Title	FILTER (functional & immunological outcomes after minimally invasive TME surgery, laparoscopic and robotic)
Internal ref. no.	
Problem statement	Rectal cancers are defined as cancers originating within 15 cm from the anal verge. Since the introduction of the TME surgery (Total Mesorectal Excision) by Heald et al in 1982, the oncological outcome of rectal cancer patients has improved significantly. ¹
	In recent years surgical techniques (and as a result the TME technique) have evolved from open techniques to several minimally invasive techniques. In TME, the laparoscopic approach is now widely accepted as having similar oncological outcomes as the open technique and having significantly better short-term outcomes, such as a shorter length of hospital admission, smaller wounds, less incidence of postoperative hernias, less intraoperative blood loss and more. ^{2–5} However, the laparoscopic approach has its own limitations, such as crowding of instruments in the small and narrow pelvis. Other surgical techniques have been introduced in an attempt to overcome these limitations, such as the transanal approach (TaTME) and the robotic approach, though superiority of either of these techniques to the laparoscopic technique has yet to be proven. ^{6–9}
	The stress response
	Every surgical intervention causes collateral damage and creates wounds which need to heal. This leads to a stress reaction of the body, which in turn releases cytokines and inflammatory mediators that cause a variety of infectious symptoms known as the SIRS reaction (Systemic Inflammatory Response Syndrome). The severity of the SIRS can be measured with blood analyses. If robotic surgery is more precise than other techniques and leads to less tissue damage during surgery, we hypothesize this could also lead to a reduced inflammatory response postoperatively, which we could measure in postoperative bloods and compare between the laparoscopic and robotic groups.
	Functional outcomes
	Rectal cancer has always been associated with a high risk of urological and sexual dysfunction due to accidental intraoperative damage to the pelvic nerves. Some have hypothesized that robotic surgery is more precise than other techniques and should lead to less intraoperative damage to nerves and vessels. If this is correct, we should observe better functional outcomes in robotic patients in terms of urological, sexual and bowel function. An earlier study conducted in Portsmouth Hospitals University NHS Trust showed a possible trend towards robotic surgery having better functional outcomes, but this study was done retrospectively and was limited to urological and sexual function. As such, we prepose to expand on this study by conducting this prospective single centre study.
	Historically most patients who underwent rectal cancer surgery received a (temporary) stoma. With the higher rate of restorative procedures, the bowel function has also become more important, as a better bowel function correlates with a higher Quality of Life. These outcomes can be assessed by using several certified questionnaires

	on various topics (sexual function, urological function, and bowel function) and comparing them between the groups.
	Robotic technology is relatively expensive to use, but there may be a trend towards improved outcomes in high-risk patients, as seemed to be the case in our previous retrospective study. 10 This could reduce the need for temporary stomas and return to theatre or readmissions, and actually result in overall cost savings compared to other techniques.
	The aim of this study would be to assess the stress response in postoperative blood samples and the functional outcomes after laparoscopic and robotic rectal cancer surgery in a prospective fashion. Our hypothesis is that robotic surgery causes less of a postoperative stress response with better or similar functional outcomes.
Research question / hypothesis	Does robotic rectal cancer surgery result in a more precise dissection with a reduced immune/stress response and does it lead to better functional outcomes as compared to laparoscopic surgery?
Study Design	Prospective single-centre cohort study
Study Participants	All patients operated for rectal cancer with curative intent using minimally invasive techniques at Queen Alexandra's Hospital in Portsmouth
Planned Sample Size	80
Follow-up duration	12 months
Planned Study Period	December 2021-December 2024
Primary Objective	 Assessment of sexual, urological and bowel function in patients undergoing rectal cancer surgery Analysing postoperative stress and immune response in blood samples
Secondary Objectives	Assessment of Quality of Life To assess the anorectal physiology after rectal cancer surgery To compare surgical process outcomes between robotic and other types of surgery To compare patient related outcomes relating to recovery between the surgical methods, i.e. length of hospital stay, early morbidity
Primary Endpoint	 Qualitative functional assessment of sexual, urological and bowel function at baseline and at 3, 6, and 12 months by using: International Prostatic Symptoms Score (IPSS) (male) International Index of Erectile Function (IIEF) (male) Female Sexual Function Index (FSFI) (female) Kings Health questionnaire (female) LARS-score (male/female) Vaizey score (male/female) Measurement of stress response by taking blood samples at baseline and post-operatively on day 1, 3 and 5. The blood will be tested on: White cell count CRP NLR (neutrophil lymphocyte ratio)

	 IL-6 IL-10 TNFa MPO (neutrophil myeloperoxidase)
Secondary Endpoints	QOL assessments by using validated questionnaires at baseline, 6 months and 12 months by using; • QLQ-C30 and QLQ-CR29 • EQ-5D Surgical process outcomes: operative time, blood loss, stoma rate, conversion rate Patient related outcomes: length of hospital stay, opioid requirements and compliance with ERP, worst vital signs post op, worst pain scores, time to flatus (in days) and return of bowel function, early morbidity (up to 30 day postoperative complications, Clavien-Dindo Classification), early mortality, adverse events. Assessing anorectal physiology by using an anorectal manometry at baseline and after 1 year (optional)
Intervention (s)	None

3. ABBREVIATIONS

AE Adverse Events

AR Adverse Reactions

ASA American Society of Anaesthesia

CI Chief Investigator
CRP C-reactive Protein

EQ-5D Euro Quality of life questionnaire

ERP Early Recovery Program

FESFI Female Sexual Function Index

IIEF International Index of Erectile Function

IL-10 Interleukine 10 IL-6 Interleukine 6

IPSS International Prostatic Symptoms Score

ISRCTN International Standard Randomised Clinical Trial Number

LARS Low Anterior Resection Syndrome

MDT Multi-disciplinary team

MPO neutrophil myeloperoxidase

NBOCAP National Bowel Cancer Audit Programme

NHS National Health Service

NIHR National Institute for Health Research

NLR Neutrophil lymphocyte ratio

PI Principal Investigator

QLQ-CR29 Quality of Life Questionnaire- Colorectal cancer module

QLQ-C30 Quality of Life Questionnaire- Cancer

QOL Quality of Life

SAE Serious Adverse Events

SAR Serious Adverse Reactions

SIRS Systematic Inflammatory Response Syndrome

TME Total mesorectal excision

TNFa Tumor Necrosis Factor alpha

4. BACKGROUND AND RATIONALE

Rectal cancers are common in the western world and make up about one quarter of all the colorectal cancers. Rectal cancers are defined as originating within 15 cm of the anal verge. 11 The primary treatment of these cancers is surgery, either with or without neoadjuvant therapy (chemo- or radiotherapy). As the surgical techniques have evolved over time, outcomes have improved. There was a time when abdominoperineal excision of the rectum was considered gold standard for low rectal cancers, despite leaving everyone with a permanent colostomy and having poor survival rates. 12 Since the introduction of the TME (Total Mesorectal Excision) technique by Heald et al. in 1982, the oncological outcome of rectal cancer patients has improved significantly. 1 During the same time as the introduction of the TME technique, in the late 80's, minimally invasive laparoscopic colorectal surgery made its debut and led to significant improvements in short-term postoperative outcomes. 2,3 This improvement of the surgical technique in combination with the advent of modern instruments has facilitated sphincter saving low and ultra-low anterior resections. Since 1992 the laparoscopic approach has been applied to rectal cancer with promising results. 4,5

The balance between oncological clearance and function preservation can be achieved with any of the four surgical approaches: open, laparoscopic, trans-anal or robotic. Although laparoscopic surgery has been widely accepted as a better alternative to open surgery in terms of short-term outcomes, its adoption in general practice for rectal cancers in the UK remains low. According to NBOCAP, 28% of the colorectal cancer patients in the UK are still treated with open surgery. The laparoscopic approach is based on a long learning curve and many of it's critics cite the high conversion rates, lack of flexibility of the instruments and limited hand-eye coordination with lack of tactile perception. In order to overcome these limitations other minimally invasive techniques, such as robotic surgery and the trans-anal approach (TaTME), were introduced as an alternative to laparoscopic surgery.

The current focus is not only on the complete clearance of neoplastic lesion, but also on preservation of the function. This is even more challenging for mid to (very) low rectal cancers, due the combination of a narrow pelvis, difficult access, and proximity of other structures. The Da Vinci robotic system was introduced to achieve an optimal functional outcome after anterior resection. The advantage Da Vinci has over the conventional laparoscopy is seven degrees of instrument movement, a fixed camera to provide stable operative view and the ability to filter out tremors. It is also less exhausting for the surgeon, who can take regular breaks to improve the surgical efficiency and perform the procedure more comfortably. The availability of robotic surgery as an option for patients is limited by the upfront expense that comes with the purchase of the systems and the subsequent maintenance costs. Additionally, there is a limited number of surgeons trained to perform complex procedures with these systems, and adequate training takes time for both the trainees and those with sufficient expertise to train others.

The debate whether robotic assisted surgery is superior to laparoscopic surgery is still ongoing. The lack of significant differences between them could be due to surgical trials being performed with robotic surgeons still in the beginning of their learning curve. In addition to this, a lot of robotic research is being done in Asian countries, which have a different population with less obesity 14–18. Because of this, the advantages of the robotic approach may be dampened as compared to operations in Western, more obese populations, which means there is still a need for ongoing research comparing the different minimally invasive techniques (in Western populations).

Every surgical intervention creates a wound, which leads to a stress response of the body with the release of cytokines and inflammatory mediators. These can cause a variety of symptoms commonly referred to as SIRS (systemic inflammatory response syndrome), which can be measured with blood analyses. The magnitude of this SIRS response is directly related to the risk of post-operative complications, such as ileus, pain and opioid requirements. It is postulated that the degree of SIRS response decreases in a stepwise fashion when the choice of approach in rectal cancer surgery moves from open to minimally invasive (laparoscopic, trans-anal and robotic).

The ability to perform a more precise dissection in robotic surgery could result in minimal tissue damage and hence reduced SIRS. With every surgery there is also a risk of accidentally damaging structures, such as vessels and nerves. Rectal cancer surgery has always been associated with a high risk of harming such structures, due to the complexity of the surgery and the small surgical field^{19–21}. Damaging the pelvic nerves can lead to severe urological, sexual and/or bowel function disorders. More and more surgeries are being performed in a restorative setup, which means the bowel function is becoming increasingly important. Studies have shown that the functional outcomes in rectal cancer patients is related to their Quality of Life outcomes^{19,20,22–24}. These functional outcomes can be assessed through several certified questionnaires on each topic (sexual function, urological function, and bowel function) and compare the outcomes. An earlier study in our hospital suggested a possible trend towards robotic surgery having better urological and sexual functional outcomes.¹⁰

Although robotic technology is expensive to use, there may be a trend towards improved outcomes in high-risk patients. A long-term improvement of functional outcomes would reduce overall costs in the long run. There's also the possibility of shorter length of hospital stay with the robot-assisted procedures, which could also save money.²⁵ Moreover, with a more precise operative technique, surgeons are less likely to use preventive temporary ileostomies. Across the UK there is a wide variation in the proportion of patients that receive a permanent stoma at surgery (7% - 83%), and around 30% of patients will have an unclosed ileostomy at 18

months.¹³ Less temporary ileostomies would significantly cut costs through fewer stoma reversal surgery, less hospital admittance, no stoma bag training and no stoma bag materials. If a small group of patients do develop a Low Anterior Rectum Syndrome, they can still receive a stoma later.

The aim of this study is to assess the post-operative stress response measured in blood in combination with functional outcomes after laparoscopic and robotic rectal cancer surgery. The study will be set up in a prospective fashion with the hypothesis that robotic surgery causes less of a stress response, along with better or similar functional outcomes.

5. PRELIMINARY STUDIES AND EXPERIENCE OF INVESTIGATORS

The literature available on the surgical stress and immunological response following surgery, and specifically rectal cancer surgery, investigate different immune markers and comparing different types of surgery, leading to mixed results. In addition to this, the studied cohorts are often too small to draw a significant conclusion from the results.

Functional outcomes

In a recent meta-analysis by Ohtani et al. the functional outcomes after rectal cancer surgery between robotic and laparoscopic surgery were compared and their sub-analysis included data from 9 articles. As depicted in the table below, the largest studies came from Asian countries. Their conclusion is that both urological and sexual dysfunction did not differ significantly between the two groups, with a Urological Odds Ratio of 0.85 (95%CI 0.57-1.26, p=0.41) and Sexual Odds Ratio of 0.54 (95%CI 0.19-1.58, p=0.26)). Most of the articles only report a short-term complication rate (<30 days) for urinary retention. These have a range of different causes, for example urinary catheter use, epidural analgesia or inflammation/swelling of the tissues. A long-term validated assessment tool, such as the IPSS questionnaire for urological function and the IIEF for sexual function, would be more insightful for the outcomes. The 3 studies that do use these methods for urological function assessment (Cho, Kim N.K. and D'Annibale) show a favourable or similar outcome for the robotic technique. The 5 studies using IIEF for sexual dysfunction show a trend towards better results for the robot, (see table 1). Two studies also mention faecal incontinence to be less severe with the use of the robot but provide no information on the methods used to assess this. 9,14–17,26–31

Table 1: Overview functional outcome articles, Ohtani meta-analysis 9,14–17,26–31

Article	Year	Country	Patients R= Robotic L= Laparoscopic	Urinary retention/ complication (<30 days)	urodynamic study (>30 days)	Sexual dysfunction /IIEF	Fecal incontinence
Alleman	2012- 2014	Swiss	R 20 L 40	1 2	-	-	-
Cho	2007- 2011	Korea	R 278 L 278	5 (1,8%) 11 (4.0%)	2 (0.7%) 12 (4.3%)	7 (2.5%) 6 (2.2%)	6 (2.2%) 3 (1.1%)
Fernandez	2002- 2012	USA	R 13 L 59	18 (53%) 5 (39%)	-	-	-
Silvia-Velazco	2010- 2014	USA	R 66 L 118	10 (15.2%) 15 (12.7%)	-	-	-
Patriti	2004- 2008	Italy	R 29 L 37	1 (3.4%) 1 (2.7%)	-	1 (5.5%) 3 (16.6%)	2 (6.8%) 1 (2.7%)
Park	2007- 2009	Korea	R 52 L 123	0 2 (1.6%)	-	-	-
Morelli	2009- 2014	Italy	R 50 L 25	4 (8%) 1 (4%)	-	-	-
Kim NK	2008- 2009	Korea	R 100/30 L 100/39	4 (4%) 9 (9%)	N > 3 mo	N > 6 mo -	-
Kim JC	2010- 2015	Korea	R 533 L 486	29 (5%) 29 (6%)	-	19.1% 25.6%	-
D'Annibale	2006- 2012	Italy	R 30 L 30	-	N > 1 y N > 1 y	N > 1 y +/- N > 1 y	-

Stress-response

Evidence on the stress response after surgery is lacking. There are a few studies on the subject, but almost none on colorectal surgery, and no systematic reviews or meta-analyses. The studies that do report colorectal surgery are summarised in table 2. The studied variables are very heterogeneous, groups are small and almost all compare open surgery with a minimally invasive technique (either robotic or laparoscopic), finding a statistically significant difference. 18,32-34

There has only been one study that compared laparoscopic colorectal surgery with robotic colorectal surgery for stress response, which is Shibata et al. ¹⁸ They compared the surgical stress response after open, laparoscopic and robotic colorectal surgery. As expected, the open group showed the highest magnitude of surgical trauma after surgery. The robotic HLA-DR had a statistically significant difference with the open group on day 3, but not with laparoscopic. CRP was slightly lower on day 6 for the robotic patients compared with laparoscopic, but wasn't statistically significant. A possible explanation for the comparable outcomes between the laparoscopic and robotic groups is that all the tumours in the robotic group were in the rectum. This is assumed to cause more surgical stress than a colon resection, which is also mentioned in the discussion of the study.

Table 2: Overview articles on stress $response^{18,32-34}$

Article	Year	Country	Approach	Surgery	Markers	Time points	Conclusion
Shibata	2012- 2013	Japan	Colorectal Open (8) Lap (23) Robot (15)	Left hemi LAR, high- AR, ISR, sigmoid	HLA-DR, CRP, Lymphocyte subset	Pre-op Day 1 Day 3 Day 6	HLA-DR: RS>OS, RS=LS CRP: OS > LS/RS, Day 1 LS <rs (non-sig)<="" 3="" 6="" day="" ls="" max="" os="" rb,="" rs<ls="" td=""></rs>
Krzystek- Korpacka	2013- 2015	Poland	Colorectal Open (31) Robot (30)	?	IL7, Lymphocyte count, Lymphocyte/ neutrophil ratio	Pre-op 8 hr 24 hr 72 hr	Lymphocyte count drop R <o and="" are="" decline="" drop="" il-7:="" il7="" increase,="" levels="" linked="" lymphocyte="" neutrophillymphocyte="" o="" pre-op="" r="" ratio<="" rise="" steady="" td="" with=""></o>

Cancer of the rectum, which is cancer in the last 15 cm of the large bowel, is a common type of cancer. The treatment for this type of cancer is taking out the whole tumour with an operation. This used to always be done with an open procedure, leaving a big scar, and is still the case for 28% of rectal cancer patients in the UK. With the rise of key-hole surgery we can do the same surgery with smaller wounds, leading to a shorter recovery time after surgery, but the standard (laparoscopic) key-hole surgery has its own limitations. An example of this is that it is hard to navigate deep in the pelvis with the current 'laparoscopic' key-hole instruments, which can lead to accidentally harming structures such as blood vessels or nerves. Harming these structures can lead to sexual dysfunction and problems with urinating or bowel control. To try and limit these unwanted side-effects other new techniques have been introduced, one of which is the robotic technique.

This robot (called 'Da Vinci') is a more flexible device with a wider range of controlled movements, is equipped with a 3D camera (leading to better vision) and allows for a more precise removal of the tumour. We think this technique will cause less harm to the surrounding structures, leading to a better outcome of the urological, sexual and bowel function.

A way to measure the harm that is done by a surgery is by measuring the stress response in blood. Every surgery causes wounds that the body needs to heal. This healing process is more severe when larger wounds are made and can be measured in the blood. We believe that with robotic surgery the size of the surgical wounds can be reduced and cause a less severe surgical stress response.

THE STUDY

This study is looking to recruit a group of 80 patients with rectal cancer who are referred to the surgical department at Queen Alexandra Hospital for a surgical resection. We will compare the standard laparoscopic operation (Total Mesorectal Excision (TME) surgery) with robotic TME surgery. To compare the surgical stress response, we will take blood samples before the surgery and on day 1, 3 and 5 after the surgery. If all goes well day 5 is usually the day a patient is discharged home after this kind of surgery. To compare the functional outcomes, we will ask the patients to complete several questionnaires on urological function, sexual function, bowel function and general quality of life at several moments: before the surgery and after 3, 6 and 12 months. The research team will also gather further information about the recovery and cancer treatment by reviewing the patient's hospital notes for 1 year. This study will not affect the surgical after care of patients in both groups. After completing this study, we will

have better insight into which operation is better at causing the least harm to the surrounding structures when removing a rectal tumour.

6. AIMS AND OBJECTIVES

6.1 Main Hypothesis

Robotic surgery for rectal cancer results in a milder stress response and similar or better functional outcomes when compared to the laparoscopic approach.

6.2 Primary Objectives

- 1. Assessment of sexual, urological and bowel function in patients undergoing rectal cancer surgery
- 2. Analysing postoperative stress and immune response in blood samples

6.3 Secondary Objectives

- 1. Assessment of Quality of Life
- 2. Assessment of the anorectal physiology after rectal cancer surgery
- 3. To compare surgical process outcomes between robotic and laparoscopic rectal surgery
- 4. To compare patient related outcomes relating to recovery between the surgical methods, such as length of hospital stay, early morbidity and others

7. STUDY DESIGN

7.1 Summary of Study Design

A prospective, single centre, observational study with qualitative assessment of sexual, urological, bowel function and stress response in patients with rectal cancer comparing robotic surgery with laparoscopic surgery.

7.2 Primary and Secondary Endpoints/Outcome Measures

Primary endpoints:

- 1. Assessment of functional outcomes by using validated questionnaires for bladder, bowel and sexual function pre-operatively, and after 3, 6 and 12 months.
 - International Prostatic Symptoms Score (IPSS) (male)
 - International Index of Erectile Function (IIEF) (male)
 - Female Sexual Function Index (FSFI) (female)
 - Kings Health questionnaire (female)
 - LARS-score (male/female) Not applicable at 3 and/or 6 months if the patient still has a stoma in situ at those respective follow-up moments
 - Vaizey score (male/female)
- 2. Measurement of stress response by taking blood samples at baseline and postoperative days 1, 3 and 5. Blood samples can be collected by anyone trained to do so and will be processed by an appropriately delegated member of the clinical team (including the research team). The following blood tests will be collected:
- White blood cell count (WBC)
- C-reactive protein (CRP)
- NLR (neutrophil lymphocyte ratio)
- IL-6
- IL-10
- TNFa
- MPO (neutrophil myeloperoxidase)

Some of the above blood tests (WBC, CRP, NLR, etc.) may be carried out as part of routine post-operative care. If these results are available, they can be used and additional sampling may not be required. Should these test results also be available for postoperative days 2 and 4, they can also be collected for use in this study, but this will be optional and no additional sampling will be done on these days.

Secondary outcomes:

- 1. Quality of life assessment using validated questionnaires (EORTC QLQ-C30/ CR29 and EQ-5D) at baseline, and after 3, 6 and 12 months.
- 2. Surgical outcomes, such as operative time, blood loss, stoma application, conversion, and intra-operative complications
- 3. Patient related outcomes:
 - a. Length of hospital stay
 - b. Opioid requirements and compliance with ERP
 - c. Worst vital signs post op
 - d. Worst pain scores
 - e. Time to flatus (in days) and return of bowel function
 - f. Early morbidity (up to 30-day postoperative complications, Clavien-Dindo Classification*)
 - g. Early mortality
 - h. Adverse events.
- 4. Optional: assessment of anorectal physiology after laparoscopic or robotic surgery in rectal cancer patients by using an anorectal manometry at baseline and after 1 year
 - a. Assessment will be done in the outpatient clinic when patients come for their standard care preoperative and 12-month follow-up visit. The manometry will be performed by the clinical team using departmental equipment.

Grade I - Any deviation from normal post-operative course without the need of pharmacological or surgical intervention

Grade II - Requires pharmacological treatment

Grade III - Requires surgical, endoscopic or radiological intervention

Grade IV - Life threatening complication/ requiring ICU management

Grade V - Death of a patient

^{*}Clavien-Dindo classifications.36

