 been internationally validated and frequently used in the current literature.
- Low Anterior Resection Syndrome, LARS this is a simple 5-question tool established in Denmark in 2012 and validated in English in 2014. This internationally validated score attempts to specifically assess function in patients undergoing low anterior resection surgery. If patients still have a stoma in situ at 3 and/or 6 months, this questionnaire will be skipped for those timepoints.
- St Marks Faecal Incontinence tool, **Vaizey score** this questionnaire was created in 1998 at St Marks hospital in the UK and allows comparison with historical data that also used the similar Wexner score and other center's published results.
- International Prostate Symptom Score, IPSS this is a simple 8-question tool that has been validated internationally and adopted as the global standard for urological

symptom scoring. **Kings Health questionnaire, KHQ,** is a 21-item questionnaire to evaluate the impact of urinary incontinence on the quality of life in women.

Sexual function questionnaires: including International Index of Erectile Function, IIEF, for males – this is a 15-question validated questionnaire which is the most widely used to assess erectile dysfunction and considered as 'gold standard' by global health entities. The Female Sexual Functional Index (FSFI) evaluates, as the name says, the sexual function in women in 19 questions.

Questionnaire completion

If patients are included in multiple studies using one or more of the same questionnaires as described above, the research team is allowed to use these answers for this study as well, rather than burdening the patient with extra unnecessary paperwork. The criteria for this are:

- The version of the forms used for the other study is the same as the version described in this study;
- The questionnaire was completed within the appropriate timeframe as described above:
- An appropriately delegated member of the research team is responsible for trans scripting the filled in form for use in this study.

If patients are for any reason unable to complete one or more of the questionnaires, these will be noted as "unknown", and the patient will remain included in the survey. Patients will have the option for retrospective completion of the baseline questionnaires with a maximum of 30 days after the previously described timeframes.

Delays in surgery

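### The stoma rule covers LARS at 3 and 6 months only; Vaizey at every visit and LARS at 12 months have none, so diverted patients' bowel scores may be uninterpretable or lost among non-responders

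*Protocol*

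**What the plan says.** Section 7.2 makes functional outcome a primary endpoint, measured with questionnaires for "bladder, bowel and sexual function pre-operatively, and after 3, 6 and 12 months". Two of the six instruments concern the bowel.

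- **LARS.** Section 7.2 qualifies it: "Not applicable at 3 and/or 6 months if the patient still has a stoma in situ at those respective follow-up moments". The questionnaire list in section 10.2 repeats this: "If patients still have a stoma in situ at 3 and/or 6 months, this questionnaire will be skipped for those timepoints". Neither place mentions a stoma still present at 12 months.
- **Vaizey.** Section 7.2 lists "Vaizey score (male/female") with nothing further. Section 10.2 describes it as the "St Marks Faecal Incontinence tool" and attaches no stoma condition.

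Other parts of the protocol that bear on this:

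- Section 4 reports that "around 30% of patients will have an unclosed ileostomy at 18" months, and says that with a more precise technique "surgeons are less likely to use preventive temporary ileostomies".
- Section 8.3 excludes planned abdominoperineal excision and Hartmann's procedure, but not an anterior resection with a diverting stoma.
- Section 10.2 has any questionnaire that a patient cannot complete noted as unknown, with the patient kept in the study. Section 13.3 rules out imputation.
- Section 13.2 plans Student's t test between groups and a paired t test of postoperative against preoperative bowel function. Neither carries a stoma condition.

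**The concern.** The protocol recognises that a stoma makes a bowel score inapplicable. It then applies that to one of two bowel tools and to two of three postoperative visits. The omitted tool measures anal incontinence, so the reasoning behind the LARS rule applies to it at least as clearly: a defunctioned patient passes essentially no stool through the anus.

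Two things can follow, and the text allows both:

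- **The form is completed.** The answers say little about continence and will probably sit near the floor of the scale. In the between-group test, the arm with more stomas looks more continent. In the paired test, a diverted patient can look improved on the preoperative score.
- **The form is noted as unknown.** The patient leaves the Vaizey data and cannot be told apart from someone who did not return the questionnaire.

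Staff could also handle similar patients differently. Because the protocol itself suggests that stoma use may depend on technique, neither outcome can be assumed to balance between the groups.

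**Working it through.** **1. The rule, visit by visit (sections 7.2 and 10.2)**

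| Tool | 3 months | 6 months | 12 months |
|---|---|---|---|
| LARS, stoma in situ | not applicable | not applicable | no rule |
| Vaizey, stoma in situ | no rule | no rule | no rule |

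Four of the six cells are open. The two sections agree with each other, and no other section fills these cells.

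**2. The plan's own sample size (section 9)**

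36 per arm with 10% loss: 36 / (1 − 0.10) = 40 per arm, or 80 in total, as stated. I use 36 per arm below as the number retained. The 36 itself cannot be checked because no SD is given, and the gap in the rule does not depend on it.

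**3. How many patients might be affected**

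The only late stoma figure in the protocol is the 30% in section 4, a UK background figure at 18 months. If it carried over to this study, 0.30 × 80 = 24 of those recruited, or 0.30 × 72 ≈ 22 of those retained, would be diverted.

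**4. If diverted patients are scored**

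Assumptions, none from the protocol: diverted score 0; undiverted mean m = 8 and SD 5 in both arms; scale 0 to 24. With stoma share s, the arm mean is (1 − s)m. With no true difference, the spurious gap between laparoscopic (L) and robotic (R) arms is m(s_L − s_R).

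| Stoma share L v R | Spurious gap, m = 8 | Range, m = 4 to 10 | False positives at P<0.05 |
|---|---|---|---|
| 30% v 30% | 0 | 0 | about 5% |
| 30% v 20% | 8 × 0.10 = 0.8 | 0.4 to 1.0 | about 9 to 10% |
| 30% v 10% | 8 × 0.20 = 1.6 | 0.8 to 2.0 | about 25% |

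The last column is from simulation: 36 per arm, normal scores clipped to 0–24, two-sided Student's t test. In these unequal examples the gap runs against the robotic arm.

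With equal shares, a true difference δ becomes (1 − s)δ. At 30% that is 0.7δ.

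**5. If diverted patients are left out**

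The number scored per arm is 36(1 − s). At s = 30% it is 36 × 0.70 = 25.2. The design's implied standardised effect is (1.96 + 0.842) × √(2/36) ≈ 0.66. At that effect, power falls from 80% to 65%, since 0.66 / √(2/25.2) − 1.96 ≈ 0.38 and Φ(0.38) ≈ 0.65. At 10%, 20% and 40% diverted it is 76%, 71% and 58%. This borrows the design's effect size; the protocol gives none for Vaizey.

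**The case against.** The best reply is that the protocol never says diverted patients are scored as continent. A reader might infer that from the missing rule, but no section says that they must complete the Vaizey, that they score 0, or that such a score is analysed. The unknown rule in section 10.2, with no imputation, could remove them instead. The tick in the assessment table does not decide it either: it covers all quality-of-life and functional questionnaires as one block, including LARS and the sex-specific tools. This part of the objection stands, so false continence is one possible result and not the stated plan.

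It does not close the gap. A diverted patient is able to fill in the form, and the authors wrote a separate LARS rule despite the general one. If the unknown rule were used, stoma patients would be mixed with non-responders.

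Three further limits also stand.

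- The 30% is a national background figure at 18 months, used in a cost argument. The protocol gives no stoma rate for this unit at any study visit.
- It would be tempting to quote much larger effects. Under the same model, 70% v 50% diverted gives about 28 to 29% false positives, but nothing in the protocol supports such shares. Nor would the Vaizey mean be mostly a count of stomas at 30%. Of the score variance, 0.3 × 0.7 × 8² = 13.4 comes from stoma status and 0.7 × 5² = 17.5 from patients without one, so stoma status accounts for 13.4 / 30.9, about 43%.
- Vaizey is one of six functional questionnaires, listed beside seven blood markers. The protocol does not define a bowel co-primary endpoint, and the sample size does not rest on Vaizey.

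Stoma application is recorded as a surgical outcome, and records are reviewed at follow-up, so status might be recovered in part. The display of stoma patients could be left to an analysis plan. Who should complete a primary-endpoint questionnaire could not: the protocol sets that rule itself and leaves it incomplete.

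**Conclusion.** The point holds as a gap in a rule that the protocol chose to fix, and it should be corrected. With a stoma in situ, LARS is not applicable at 3 and 6 months, but nothing is said for LARS at 12 months or for Vaizey at any visit. The resulting values may be uninterpretable or indistinguishably missing, possibly unequally by group.

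The gap is certain from the text; its size is not. On the stated assumptions, the cost of scoring diverted patients runs from no bias with a diluted difference (equal shares) to a 1.6-point artefact (30% v 10%). The cost of leaving them out is fewer scores and a hidden reason for their absence. The protocol supports neither the claim that diverted patients will be analysed as continent nor a definite bias against robotic surgery. The direction depends on which arm has more stomas and on how the forms are handled.

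**What to change.** In sections 7.2 and 10.2, replace the LARS-only wording with one rule: LARS and Vaizey are both not applicable at any postoperative visit, including 12 months, while a stoma is in situ. Record stoma status with each questionnaire. At each visit, report by group the number with a stoma in situ, separately from non-response, beside the scores of patients with restored continuity.

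The cost is about two sentences in the protocol and one tick-box per questionnaire. There will be fewer Vaizey values per visit, and the comparison will apply to patients with restored continuity and not to everyone operated on. If the stoma share differs by group, that restriction is itself selective, which is why the stoma counts must be shown alongside the scores.
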